**Table 4 Collection and Reporting of Adverse Events and Lack of Efficacy**

Adverse Event criteria	Electronic case record form (eCRF) only	Paper form only	Electronic case record form (eCRF) + Paper form
Non serious	Non drug related lack of efficacy reports with associated signs or symptoms or clinical sequelae	Drug related lack of efficacy reports without associated signs or symptoms or clinical sequelae.	Drug related lack of efficacy with associated signs or symptoms or clinical sequelae
Serious	Non drug related lack of efficacy reports with associated signs or symptoms or clinical sequelae	Drug related lack of efficacy reports without associated signs or symptoms or clinical sequelae.	Drug related lack of efficacy reports with associated signs or symptoms or clinical sequelae

The investigator will then record all relevant information regarding an AE/SAE in the electronic CRF “and/or paper form as applicable

For lack of efficacy reports the paper form will be used to submit to GSK as per [Table 4](#).

**All paper forms are required to be faxed to GSK Canada's Drug Safety department at PPD within 24 hrs of first awareness.**

**Description:**

- The purpose of this RAP is to describe the planned analyses and output to be included in the Clinical Study Report (CSR) for Protocol 207040.
- This RAP is intended to describe the study population, efficacy and safety analyses required for the study.
- This RAP will be provided to the study team members to convey the content of the final Statistical Analysis Complete (SAC) deliverable.

## 1. INTRODUCTION

The purpose of this reporting and analysis plan (RAP) is to describe the analyses to be included in the Clinical Study Report (CSR) for Protocol 207040 [GlaxoSmithKline Document Number: 2016N307903\_01 (Dated: 10SEP2018)].

Revision Chronology:		
2016N307903_00	22-JUN-2017	Original
2016N307903_01	10-SEP-2018	Amendment 1

All data displays (Tables, Figures & Listings) will use the term “Subject” which reflects CDISC and GSK Data Display Standards terminology.

## 2. SUMMARY OF KEY PROTOCOL INFORMATION

### 2.1. Changes to the Protocol Defined Statistical Analysis Plan

Changes from the planned statistical analysis specified in protocol amendment 1 are outlined in [Table 1](#).

**Table 1 Changes to Protocol Defined Analysis Plan**

Protocol	Reporting & Analysis Plan	
Statistical Analysis Plan	Statistical Analysis Plan	Rationale for Changes
Duration of run-in included in analysis models as a continuous covariate, measured in days.	Duration of run-in included in analysis models as a categorical covariate of number of visits.	Participants can complete the run-in period in 1, 2 or 3 visits, use of a categorical covariate is more flexible than the assumption of a linear relationship.
Missing data due to a medical device incident will be assumed to be missing at random within the last 3 months treatment period.	Missing data due to a medical device incident will be assumed to be missing at random within each month of the treatment period.	Monthly adherence rates are used within the imputation model to allow for variation in adherence over time.
Participants who prematurely discontinue from study will have their post-withdrawal daily adherence data imputed using data from the control arm	Participants who prematurely discontinue from use of the ELLIPTA maintenance sensor will have subsequent adherence data imputed using data from the control arm	The ELLIPTA maintenance sensor may be discontinued without withdrawal from the study
Protocol Section 11.3 Populations for Analyses	RAP Section 4 Analysis Populations	The analysis populations have been updated to follow the study populations standard definitions and statistical displays

Protocol	Reporting & Analysis Plan	
Statistical Analysis Plan	Statistical Analysis Plan	Rationale for Changes
	Mean change from baseline (Randomisation) in ASUI and SGRQ total score at Month 6 included in the RAP as an additional endpoint	To support the exploratory summaries and analyses for ASUI and SGRQ continuous endpoint
Composite endpoint - Percentage of patients who have either an ACT total score of $\geq 20$ or an increase from baseline of $\geq 3$ in ACT total score at Month 6 (Visit 10).	Composite endpoint - Percentage of patients who have either an ACT total score of $\geq 20$ and/or an increase from baseline of $\geq 3$ in ACT total score at Month 6 (Visit 10).	The condition 'and/or' will be applied to the composite ACT endpoint to replace 'or' to clarify that participants who achieve both an ACT total score of $\geq 20$ and an increase from baseline of $\geq 3$ in ACT total score at Month 6, in addition to those who only achieve one, will be considered a responder.
	Change from baseline (Visit 2, 3 or 4) in FeNO measured at Month 1 (Visit 5) and Month 6 (Visit 10)	To support the exploratory summary of impact of adherence on the biomarker Fractionated Exhaled Nitric Oxide (FeNO)

## 2.2. Study Objectives and Endpoints

[figure not shown]
Objectives	Endpoints
Primary Objectives	Primary Endpoints
To compare the effect of 6 months use of the CIS on adherence to ELLIPTA maintenance therapy when both the participant and the HCP are supplied with data from the maintenance sensor versus no data supplied to the participant and HCP (Arm 1 vs Arm 5)	Percentage of ELLIPTA doses taken (daily adherence  ) between the beginning of month 4 and the end of month 6 as determined by the maintenance sensor
Secondary Objectives	Secondary Endpoints
To compare the effect of 6 months use of the CIS on adherence to ELLIPTA maintenance therapy for the following aspects of the CIS: 
 
Maintenance data only supplied to participants versus no data supplied to the participant (Arm 2 vs Arm 5)
 
Rescue and Maintenance data supplied to participant and HCP versus no data supplied to the participant and HCP (Arm 3 vs Arm 5)
 
Rescue and Maintenance data only supplied to participant versus no data supplied to the participant (Arm 4 vs
 
	
 
Percentage of ELLIPTA doses taken (daily adherence) between the beginning of month 4 and the end of month 6 as determined by the maintenance sensor
 

Objectives	Endpoints
Arm 5)	
To compare the effect of the CIS on adherence to ELLIPTA maintenance therapy of the individual CIS treatment arms versus no data supplied to the participant and HCP.	
 
Percentage of ELLIPTA doses taken (daily adherence) between the beginning of month 1 and the end of month 3
 
Percentage of ELLIPTA doses taken (daily adherence) between the beginning of month 1 and the end of month 6
 

To evaluate the effect of 6 months use of the CIS on a participant's rescue medicine usage	
 
Percentage of rescue free days measured between the beginning of month 4 and the end of month 6 as determined by the rescue sensor records of date, time, and number of inhaler actuations.
 
Total rescue use measured between the beginning of month 4 and the end of month 6 as determined by the rescue sensor records of date, time, and number of inhaler actuations.
 

To evaluate the effect of 6 months use with the CIS on a participant's asthma control	
 
Change from baseline (Randomisation) in ACT total score at Month 6, measured at baseline (Visit 2, 3 or 4) and Month 6 (Visit 10)
 
Percentage of patients becoming controlled as defined as an Asthma Control Test score <math>\geq 20</math> at Month 6 (Visit 10)
 
Percentage of patients with an increase from baseline <math>\geq 3</math> in ACT total score at Month 6 (Visit 10)
 
Composite endpoint - Percentage of patients who have either an ACT total score of <math>\geq 20</math> and/or an increase from baseline of <math>\geq 3</math> in ACT total score at Month 6 (Visit 10).
 

Exploratory and Other Objectives	Exploratory Endpoints
To evaluate the effect of 6 months use of the CIS on adherence to ELLIPTA maintenance therapy on the following aspects of the CIS: 
 
HCP having access to sensor data
 
Rescue Medication data being available
 
	
 
Percentage of ELLIPTA doses taken (daily adherence) between the beginning of month 4 and the end of month 6 as determined by the maintenance sensor
 

 
To evaluate the effect of 6 months use with CIS on health care utilisation
 
	
 
Health care utilisation endpoints will include the following and will be collected from a participant's medical records. 
 
Number of outpatient visits relating to asthma
 
Number of primary care visits relating to study HCP dashboard review (for relevant study arms)
 
Number of and duration of hospitalisations, and ER visits due to asthma
 
Annualised rate of severe exacerbations
 
Number of unscheduled visits to primary care related to Asthma
 
 
 

To evaluate the effect of 6 months use with CIS on the following patient reported	
 
Percentage of patients meeting a responder threshold of <math>\geq 0.09</math> points improvement from baseline
 

Objectives	Endpoints

outcomes (PROs):
 
 
• Asthma Symptom Utility Index (ASUI)
 
• St Georges Respiratory Questionnaire (SGRQ)
 
• Patient Activation Measure (PAM)
 
• Medication Adherence Report Scale for Asthma (MARS-A)
 
• Beliefs in Medicine Questionnaire (BMQ).
 
	
(Randomisation) for the ASUI total score at Month 6
 
 
• Mean change from baseline (Randomisation) in ASUI total score at Month 6
 
• Percentage of patients meeting a responder threshold of <math>\geq 4</math> points improvement from baseline (Randomisation) for the SGRQ total score at Month 6
 
• Mean change from baseline (Randomisation) in SGRQ total score at Month 6
 
• Mean change from baseline (Screening) in PAM total score at Month 6
 
• Mean change from baseline (Screening) in MARS-A total score at Month 6
 
• Mean change from baseline (Screening) at Month 6 in BMQ: 
 
◦ General Benefit score
 
◦ General Harm score
 
◦ General Overuse score
 
◦ Specific Necessity score
 
◦ Specific Concern score
 
 
 

 
• To assess the reliability and usability of the CIS
 
• To explore impact of adherence on the biomarker Fractionated Exhaled Nitric Oxide (FeNO)
 
	
 
• Incidence of Medical Device Incidents between the beginning of Month 1 and the end of Month 6.
 
• FeNO at Screening (Visit 1), Randomisation (Visit 2,3 or 4), Month 1 (Visit 5) and Month 6 (Visit 10).
 
• Change from baseline (Visit 2, 3 or 4) in FeNO measured at Month 1 (Visit 5) and Month 6 (Visit 10)
 

 
• To explore impact of adherence on the physiological marker Peak Expiratory Flow (PEF)
 
	
 
• PEF at Screening (Visit 1), Randomisation (Visit 2,3 or 4), Month 1 (Visit 5) and Month 6 (Visit 10).
 
• Change from baseline (Visit 2, 3 or 4) in PEF measured at Month 1 (Visit 5) and Month 6 (Visit 10)
 

 
• To characterize patient experience of the CIS for participants
 
	
 
• Exit Questionnaires at Month 6 (Visit 10)
 
• Exit Interviews for a sub set of participants at Month 6 (Visit 10)
 

Safety Objectives	Safety Endpoints

To evaluate the incidence of SAEs, Non-Serious Adverse Events that lead to withdrawal from study and Non-Serious Adverse Drug Reactions in asthmatic participants using the CIS
	
 
• SAEs, Non-Serious Adverse Events that lead to withdrawal and Non-Serious Adverse Drug Reactions
 

1. Daily adherence is defined as the participant taking one dose of Relvar/Breo ELLIPTA, within a 24-hour period, starting at 12.00am each day

## 2.3. Study Design

Overview of Study Design and Key Features	
	[GlaxoSmithKline Document Number 2016N307903_01 ].
Time & Events	Refer to Appendix 1 : Schedule of Activities
Treatment Assignment	
All randomised participants will receive Relvar/Breo ELLIPTA, at the dose allocated at the run in. Salbutamol Metered Dose Inhaler (MDI) rescue medication will be prescribed to participants to use as needed throughout the study for relief of asthma symptoms as per usual practice
 
All participants will have sensors attached to both their Relvar/Breo ELLIPTA and salbutamol MDI. It is the type of data provided by the CIS (either Relvar/Breo ELLIPTA alone or Relvar/Breo ELLIPTA and salbutamol MDI), as well as who sees that data, (participant alone or participant and HCP), that defines the treatment arms.
 
Participants will be randomized 1:1:1:1:1 to one of the five treatments arms for the duration of the treatment period:
 

• Arm 1: Data on Maintenance use supplied to Participant (app) and HCP (dashboard)

• Arm 2: Data on Maintenance use supplied to Participant (app)

• Arm 3: Data on Maintenance and Rescue use supplied to Participant (app) and HCP (dashboard)

• Arm 4: Data on Maintenance and Rescue use supplied to Participant (app)

• Arm 5: No data supplied to Participant or HCP

 
The treatment period for the study is 6 months. However, due to the flexible run in period a participant could be on the study for approximately 7, 8 or 9 months in total.
 
GSK RandAll NG will be used to generate the randomisation schedule. Centralized randomisation will be used. GSK RAMOS NG will be used for treatment allocation.

## 2.4. Statistical Hypothesis

The main purpose of the study is to compare the effect of 6 months use with the Connected Inhaler System (CIS) on adherence to Relvar/Breo ELLIPTA maintenance therapy with adherence to Relvar/Breo ELLIPTA maintenance therapy without CIS use (sensor alone), in participants with poorly controlled asthma.

All participants receive Relvar/Breo ELLIPTA, either at the dose they are already prescribed or at the equivalent dose to their current ICS/LABA maintenance therapy if switched onto Relvar/Breo ELLIPTA at enrolment. All participants will have sensors attached to both their Relvar/Breo ELLIPTA and Salbutamol MDI. It is the type of data provided by the CIS (either Relvar/Breo ELLIPTA alone or Relvar/Breo ELLIPTA and salbutamol MDI), as well as who sees that data (participant alone or participant and HCP) that defines the treatment arms.

This study aims to demonstrate the superiority of the CIS on adherence to Relvar/Breo ELLIPTA with an app compared to Relvar/Breo ELLIPTA (with sensor alone).

The primary endpoint is mean percentage of ELLIPTA doses taken (daily adherence) between Months 4 and 6 as determined by the maintenance sensor daily adherence over the last three months of the study period (between months 4 to 6).

The test for the primary treatment comparison will be a test between Arm 1 versus Arm 5. This will be based on a two-sided hypothesis testing approach: the null hypothesis is the difference between Arm 1 and Arm 5 is equal to zero. The alternative hypothesis is that the difference is not equal to zero. The hypotheses associated with the statistical test of the primary endpoint are written below:

$$H_0: T_i - T_j = 0$$

(where  $i = \text{Arm 1}$  and  $j = \text{Arm 5}$ ) The null hypothesis: that the difference in response between Arm 1 and Arm 5 is zero.

$$H_a: T_i - T_j \neq 0$$

The alternative hypothesis: that the difference is not zero.

Other comparisons of interest for the primary endpoint are the individual comparisons of Arms 2, 3 and 4 with Arm 5 in order to obtain estimated mean treatment differences, 95% confidence intervals (CIs) and p-values. This will be a descriptive comparison to inform on the relative benefits of the individual aspects of the CIS and no formal inference is planned.

The effect on adherence to maintenance therapy between arms with HCP and no HCP interaction i.e. Arm 1 v Arm 2 and Arm 3 v Arm 4, and arms with rescue medication use feedback versus none i.e. Arm 1 v Arm 3 and Arm 2 v Arm 4, will be also assessed.

The comparisons of interest for the other secondary and safety endpoints are as stated above for the primary endpoint. Arms 1, 2, 3 and 4 will be individually compared to Arm

5, as relevant to the endpoint, to obtain estimated mean treatment differences, 95% confidence intervals and p-values. This will be a descriptive comparison and no formal inference is planned.

### **3. PLANNED ANALYSES**

To minimize the risk of breaking the study blind during the pre-programming of analysis datasets and displays for the final analyses, an unblinded team of programmers will scramble the data in a secure area according to a pre-defined blinding strategy, before releasing to Clinical Statistics and Programming (S&P).

#### **3.1. Interim Analyses**

An interim analysis was originally planned to be conducted when 50% of subjects complete 6 months of study treatment in order to conduct a sample size re-estimation. However the requirement for the interim analysis and sample size-re-estimation was decided no longer necessary and removed from the study protocol.

#### **3.2. Final Analyses**

The final planned analyses will be performed after the completion of the following sequential steps:

1. All participants have completed the study or have been withdrawn as defined in the protocol.
2. All required database cleaning activities have been completed and final database release (DBR) and database freeze (DBF) has been declared by Data Management (DM).
3. System Independent (SI) data to Study Data Tabulation Model (SDTM) data conversion has completed by Conversion Service Provider at Source Data Lock (SDL).
4. All criteria for unblinding the randomisation codes have been met.
5. Randomisation codes have been distributed according to RandAll NG procedures. Release of randomisation code, unblinding of study treatment and participant level treatment of SDTM data, and related quality control activities have been completed by S&P.
6. DBF on SDTM datasets has been declared by DM upon receipt of the final, treatment unblinded SDTM data from S&P.

## 4. ANALYSIS POPULATIONS

Population	Definition / Criteria	Analyses Evaluated
All participants	
 
• All participants who signed the ICF
 
	Study Population
Screened	
 
• All participants who were screened for eligibility.
 
	Study Population
Enrolled	
 
• All participants who passed screening and entered the study. Included are: Run-in Failures; Randomized Participants
 
 
Note screening failures are excluded from the Enrolled population as they did not enter the study.
	Study Population Safety
Randomized	
 
• All participants who were randomly assigned to a treatment arm in the study.
 
• This population will be based on the treatment arm the participant was randomised to.
 
	Study Population
Intent-To-Treat (ITT)	
 
• The ITT population comprises all randomised participants, excluding those who were randomised in error. A participant who is recorded as a screen or run-in failure but is randomised, and does not receive a dose of study treatment, is considered to have been randomised in error. Any other participant who received a randomisation number will be considered to have been randomised.
 
• This population will be based on the treatment arm the participant was randomised to.
 
	Study Population Efficacy (ELLIPTA Adherence, Rescue Medications Use, PRO, PEF and FeNO) Safety

Refer to Section [10.8 Appendix 8](#): List of Data Displays which will detail the population used for each display.

### 4.1. Protocol Deviations

This dataset will be the basis for the summaries and listings of protocol deviations. A separate summary and listing of all inclusion/exclusion criteria deviations will also be provided. This summary will be based on data as recorded on the inclusion/exclusion page of the eCRF.

## 5. CONSIDERATIONS FOR DATA ANALYSES AND DATA HANDLING CONVENTIONS

### 5.1. Study Treatment & Sub-group Display Descriptors

Treatment Group Descriptions										
	Relvar/Breo ELLIPTA Sensor Data Available to		Salbutamol/Rescue MDI Sensor Data Available to		RandAll NG Randomisation System			Data Displays for Reporting		
Arm	Participant	HCP	Participant	HCP	Code	Description		Full Description	Short Description	Order in Table, List, Figure (TLF)
1	X	X			1	Data on Maintenance use supplied to Participant (app) and HCP (dashboard)		Arm 1: Maintenance use data supplied to Participant and HCP	Arm 1	1
2	X				2	Data on Maintenance use supplied to Participant (app)		Arm 2: Maintenance use data supplied to Participant	Arm 2	2
3	X	X	X	X	3	Data on Maintenance and Rescue use supplied to Participant (app) and HCP (dashboard)		Arm 3: Maintenance and Rescue use data supplied to Participant and HCP	Arm 3	3
4	X		X		4	Data on Maintenance and Rescue use supplied to Participant (app)		Arm 4: Maintenance and Rescue use data supplied to Participant	Arm 4	4
5					5	No data supplied to Participant or HCP		Arm 5: No data supplied to Participant or HCP	Arm 5	5

Arm 1: Maintenance use data supplied to Participant and HCP, Arm 2: Maintenance use data supplied to Participant, Arm 3: Maintenance and Rescue use data supplied to Participant and HCP, Arm 4: Maintenance and Rescue use data supplied to Participant, Arm 5: No data supplied to Participant or HCP.

All participants will have sensors attached to both their Relvar/Breo ELLIPTA and Salbutamol (albuterol) MDI. It is the type of data provided by the CIS (either Relvar/Breo ELLIPTA alone or Relvar/Breo ELLIPTA and salbutamol MDI), as well as who sees that data (participant alone or participant and HCP) that defines the treatment arms. See Section [5.1](#) Study Treatment & Sub-group Display Descriptors for a description of what data is fed back to whom for each treatment arm, and the treatment group descriptors.

Where possible the full description will be used in data displays. If it is necessary to use the short description, for example in figure legends, the footnote shown under the table in Section [5.1](#) Study Treatment & Sub-group Display Descriptors will be included. Where treatment comparisons are included in a data display and the full treatment descriptions do not also appear within the display, the same footnote will be included.

## **5.2. Baseline Definitions**

Baseline adherence will be the percentage of ELLIPTA doses taken (daily adherence) during the last 28 days of the run-in period prior to randomisation. This will be determined using the randomisation date. A minimum of 14 run-in days prior to randomisation will be required to determine baseline adherence otherwise it will be set to missing. Any missing intermittent daily adherence data will be imputed as non-adherent i.e. the participant will be assumed to have not taken their treatment within the 24-hour time period/window, where there is no evidence of a medical device incident having occurred. Missing data due to a medical device incident such as,

- device failure
- technical failure of the ELLIPTA maintenance sensor
- data transmission failure,

will be assumed to be missing at random (MAR). For each participant the baseline percentage adherence measure will be calculated as the number of days a participant is adherent divided by the number of days without medical device incident within the baseline assessment period \* 100. See Section [10.2.2](#) Definitions of Assessment Windows for Adherence and Rescue Medication Use Analyses, for the definition of the baseline assessment period.

Baseline rescue free days will be the percentage rescue free days (RFDs) during the last 28 days of the run-in period prior to randomisation. This baseline will be determined in the same manner as the adherence baseline.

Where baseline assessments are determined from the randomisation visit, no unscheduled assessments will be considered as the baseline value.

Where baseline assessments are determined from the screening visit, Visit 1 will be used and no unscheduled screening visits will be considered as the baseline value.

If time is not collected, Day 1 assessments are assumed to be taken prior to first dose and used as baseline.

Parameter	Study Assessments Considered as Baseline			Baseline Used in Data Display
	Visit 1 Screening	Study Days -28 to -1	Randomisation Visit, Study Day 1 (Pre-Dose)	
Efficacy				
ELLIPTA Adherence Endpoints (%)		x		% adherence from Day -28 to Day -1
Rescue Free Days (RFDs) (%)		x		% RFDs from Day -28 to Day -1
Total Rescue Use (TRU) (puffs)		x		Total use from Day -28 to Day -1
ACT Total score			x	Randomisation
SGRQ Total score			x	Randomisation
ASUI Total score			x	Randomisation
PAM-13 Total score	x			Screening
BMQ Total score	x			Screening
MARS-A Total score	x			Screening
PEF (litres/minute)			x	Randomisation - use maximum value at visit
FeNO (parts per billion)			x	Randomisation - use maximum value at visit

Notes:

- Day 1 is referenced as Day 0 (Randomisation visit at either Visit 2 or 3 or 4) in Section 2.3 and Section 10.1 [Appendix 1](#): Schedule of Activities but will be reported as Day 1 per Clinical Data Interchange Standards Consortium (CDISC) reporting guidelines.
- Unless otherwise stated, if the baseline for an endpoint is missing it will not be imputed using a different timepoint or derivation but will remain missing.

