#### **7.1.3. Population of Interest**

The primary efficacy analysis will be based on the Intent-To-Treat population.

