**Table 3**

Intercurrent Event Estimation Rules (to be applied sequentially)	Intercurrent Event (IE)	Strategy with Rationale	Estimation Method following IE
1	
None (completed as randomised)
 
Without discontinuation of CIS feedback or ELLIPTA maintenance sensor
 
 
Premature discontinuation from rescue/salbutamol MDI sensor
 
Change of dose of ELLIPTA
 
 
Discontinuation of CIS feedback, but not ELLIPTA maintenance sensor
 
 
Premature discontinuation from App and/or HCP interaction
 
	
Treatment policy:
 
Directly assessed using observed adherence data while ELLIPTA maintenance sensor is in use, regardless of whether the CIS feedback is discontinued.
	Data are available; no imputation required
2	Discontinuation of ELLIPTA maintenance sensor only	
Treatment policy:
 
Without the ELLIPTA maintenance sensor, no CIS feedback is possible, assume
 
 
participants continue to take ELLIPTA as
 
	Jump to Reference (J2R) Imputation

Intercurrent Event Estimation Rules (to be applied sequentially)	Intercurrent Event (IE)	Strategy with Rationale	Estimation Method following IE
		
they would have without the CIS intervention
 
 
adherence will be like that in the control (no CIS feedback) group
 
	
3	Discontinuation of ELLIPTA	Whilst on treatment:	Follow-up after ELLIPTA discontinuation is excluded, i.e. no data; adherence is weighted by proportion of months 4 to 6 for which data is included*
4	Premature withdrawal from the study, not related to ELLIPTA discontinuation or CIS, and concurrent with discontinuation of the ELLIPTA maintenance sensor	Hypothetical:	Missing at Random (MAR) Imputation

* Discontinuation of ELLIPTA prior to the start of month 4 will lead to a participant being excluded from the primary analysis
			

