### 7.1.5.1. Statistical Methodology Specification

Endpoint / Variables
The primary endpoint is the percentage of ELLIPTA doses taken (daily adherence) between the beginning of Month 4 and the end of Month 6 as determined by the maintenance sensor. Daily adherence is defined as the participant taking one dose of Relvar/Breo ELLIPTA within a 24 hour period, starting at 12.00am each day of treatment period.
Multiple Imputation Specification
Imputation will be carried out using monthly adherence rates for months 1 to 6. 1000 draws will be used. For each draw, four intermediate imputation datasets will be created to allow for the handling of fully unobserved months (using set A imputations) and partially unobserved months (using set B imputations).

 
• Set A where the partially observed month is directly estimated under the MAR assumption as the proportion of the number of days a participant is adherent divided by the number of days data provided in that month. 
 
• J2R imputations
 
• MAR imputations
 
 
 
• Set B where the partially observed month is set to missing. 
 
• J2R imputations
 
• MAR imputations
 
 
 

The timing of the intercurrent events of discontinuation of the ELLIPTA maintenance sensor, discontinuation of ELLIPTA and withdrawal from study will be used to identify the proportion of each month to be assigned as observed data, J2R imputed data, MAR imputed data, or no data. The strategy for handling intercurrent events is described in Section 7.1.4 Strategy for Intercurrent (Post-Randomisation) Events.
 
Within each imputation draw, for each month, the observed and any imputed data will be combined to provide a percentage adherence value. The values for months 4 to 6 will be combined to create the value for the primary analysis and the weight to be assigned to each participant.
 
Multiple imputation using Rubin's rules will be used to estimate the treatment effect and associated standard error, by performing the ANCOVA analysis described below on the primary endpoint within each dataset.
 
The multiple imputation will be implemented using the methods described in Carpenter, 2013, using the macros available from https://missingdata.lshtm.ac.uk/2017/04/06/gsk-five-macros/.

Model Specification

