
The analysis will be performed on the percentage adherence between Months 4 and 6 using an Analysis of Covariance (ANCOVA) model allowing for effects due to randomised treatment arm, baseline adherence, duration of run-in (visits), country, gender, and age (years).
 
Baseline adherence will be the percentage ELLIPTA doses taken (daily adherence) during the last 28 days of the run-in period prior to randomisation. Randomised treatment arm, duration of run-in (visits), country, and gender will be included as categorical covariates; baseline adherence and age (years) will be included as continuous covariates.

Each participant will be weighted by the proportion of months 4 to 6 for which data is included in the percentage adherence endpoint (both observed and imputed data are accounted for in the weighting).

Data from all 5 treatment arms will be included in the model and used to estimate the difference between Arm 1 and Arm 5 for the primary objective.

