**Table 5 Sensor Data Assessment Windows**

Sensor Data Assessment Windows		
Analysis Month	Analysis Period	
	Beginning Timepoint	Ending Timepoint
Baseline	Latest of either Day -28 or day after Visit 1 (minimum of 14 days must be present to create a baseline)	Day -1 (Day prior to randomisation)
1	Day 1 (Day of randomisation)	Day 28 or discontinuation from adherence/rescue assessment if within month 1
2	Day 29	Day 56 or discontinuation from adherence/rescue assessment if within month 2
3	Day 57	Day 84 or discontinuation from adherence/rescue assessment if within month 3
4	Day 85	Day 112 or discontinuation from adherence/rescue assessment if within month 4
5	Day 113	Day 140 or discontinuation from adherence/rescue assessment if within month 5
6	Day 141	Earliest of either day of visit 10, Day 168 or discontinuation from adherence/rescue assessment if within month 6 if participant is a completer  OTHERWISE  Day 168 or discontinuation from adherence/rescue assessment if within month 6
Note: 'Discontinuation from adherence/rescue assessment' occurs at the earliest of premature discontinuation from use of the ELLIPTA /MDI sensor, premature discontinuation of ELLIPTA (for adherence measures), or premature withdrawal from the study.		

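### A missing baseline adherence value stays missing but is a required covariate, so any such ITT participant would drop out of the primary ANCOVA by default

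*SAP*

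**What the plan says.** SAP 5.2 (Baseline Definitions) measures baseline adherence over the last 28 run-in days and sets a floor: "A minimum of 14 run-in days prior to randomisation will be required to determine baseline adherence otherwise it will be set to missing". Table 5 in SAP 10.2.2 repeats it: "minimum of 14 days must be present to create a baseline". Neither place says whether these are calendar days or days with usable sensor data. The denominator of the baseline percentage is the number of days free of a device incident, so the value is also undefined if every baseline day is lost to incidents.

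The notes to 5.2 add that, unless stated elsewhere, "if the baseline for an endpoint is missing it will not be imputed using a different timepoint or derivation but will remain missing". No exception is stated for adherence or for rescue-free days, and the missing-data appendix (SAP 10.6.2) has no entry for a missing baseline.

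For the primary model, SAP 7.1.5.1 says "baseline adherence and age (years) will be included as continuous covariates". The same section describes the imputation: "Imputation will be carried out using monthly adherence rates for months 1 to 6". SAP 7.1.3 says "The primary efficacy analysis will be based on the Intent-To-Treat population", and SAP 4 gives the definition: "The ITT population comprises all randomised participants, excluding those who were randomised in error". That definition has no baseline requirement.

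**The concern.** A linear model cannot use a record whose covariate is missing. The plan takes 1000 imputation draws to keep people whose outcome is incomplete. It gives no rule to keep someone whose month 4 to 6 adherence was fully observed but whose sensor failed before randomisation. If that happens, the number analysed is smaller than the ITT number, for a reason the SAP does not disclose. The sensitivity GLM uses the same covariates, so it would lose the same people and could not show the effect. The secondary and exploratory adherence models and the rescue-free-days ANCOVA share the gap.

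At stake are some precision, a correct description of who was analysed, and a handling rule fixed before results are seen. The last matters more than usual because the trial is open label (Protocol 7.6).

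**Working it through.** **Does exclusion follow from the text?**

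1. Baseline can be missing (SAP 5.2, Table 5).
2. By default it stays missing (SAP 5.2, notes).
3. It is a covariate in the primary ANCOVA (SAP 7.1.5.1).
4. The imputed variables are the adherence rates for months 1 to 6 (SAP 7.1.5.1 and 10.5.3.1). Baseline is not among them.
5. A record without baseline therefore cannot be fitted. Exclusion is the default consequence of steps 1 to 4, although no sentence states it.

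**How often could baseline be missing?** V1 is at Day -28 and V2 has a window of ±2 days (schedule of activities), so V1 to V2 spans 26 to 30 days. The baseline window runs from the later of Day -28 and the day after V1, to Day -1:

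- shortest: 26 − 1 = 25 days
- on time: 28 − 1 = 27 days
- longest: 30 − 1 = 29, capped at 28 days

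If the run-in starts 7 days after screening (allowed in Protocol 5.1) and V2 is still timed from V1, 26 − 7 = 19 run-in days remain. All of these exceed 14. Run-in gaps without a device incident count as non-adherent and do not make baseline missing. The remaining routes are:

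- randomisation well ahead of schedule;
- device incidents on every baseline day;
- if the 14 days must be usable days, at least 12 incident days out of 25 (25 − 12 = 13), or 15 out of 28 (28 − 15 = 13), which is roughly half the window.

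**The protocol's own power figure.** Inputs from Protocol 11.2.1 are: difference 15, SD 28, 76 per arm, two-sided 5%. The standard error is 28 × √(2/76) = 4.54 and 15/4.54 = 3.30. Power is 91.0% by the normal approximation and 90.7% by noncentral t, against the stated value of about 90%. Also 380/(1 − 0.12) = 432 randomised, as stated.

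**Cost if a share f is lost.** With n = 76 × (1 − f) per arm and the same noncentral-t formula:

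| Assumed share without baseline | Lost of 380 | n per arm | Power |
|---|---|---|---|
| 0% | 0 | 76.0 | 90.7% |
| 2% | 7.6 | 74.5 | 90.1% |
| 5% | 19.0 | 72.2 | 89.2% |
| 8% | 30.4 | 69.9 | 88.2% |

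The shares are assumptions; the documents give none. Like the protocol's calculation, the table ignores the precision gained by adjusting for baseline.

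**The case against.** The strongest reply is that the SAP nowhere says these participants are excluded. The only exclusion it states is a different one: "Discontinuation of ELLIPTA prior to the start of month 4 will lead to a participant being excluded from the primary analysis". The note in 5.2 is a default that bars substitution from another timepoint or derivation. It does not address mean or model-based handling of a covariate. Both points stand. A reader might infer that the SAP orders the exclusion or forbids all imputation of baseline; the text supports neither. It leaves no route by which such a participant stays in.

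A reader might also suppose that baseline is a covariate in the imputation model. The imputation specification lists no covariates. Only the general wording on models in SAP 5.4.1 could suggest it, and the point does not need it.

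The trigger is narrow, and this stands too: on-schedule participants clear 14 calendar days comfortably. The power loss is small, and starting from 76 per arm is pessimistic. The protocol randomises 432/5 = 86.4 per arm, and Amendment 01 reports a lower dropout than expected. With no other losses, 86.4 × 0.92 = 79.5 per arm gives about 92% power.

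The planned tables would also partly reveal the problem. The shells for Tables 2.01 and 2.02 show baseline n and analysed n by arm against N, and the adherence listing gives device-incident days per participant. They would show the shortfall but not prevent it.

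**Conclusion.** The point holds as a default consequence of the plan. An ITT participant without a baseline value would leave the primary analysis and the sensitivity GLM even with full month 4 to 6 data, contrary to the stated population. The size is small: at most about 2.5 power points (90.7% to 88.2%) across assumed losses up to 8%, and the true share is unknown and probably low.

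Two stronger readings go too far. One is that the primary analysis is not ITT for this reason. That is true only if at least one baseline is missing, and the documents give no count. The stated exclusion for stopping ELLIPTA before month 4 is a plainer departure from full ITT. The other is that the Arm 1 versus Arm 5 contrast would be biased. Baseline is recorded before randomisation, when neither subject nor HCP sees sensor data, so the assigned arm cannot cause it to be missing.

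The change is still worth making: it costs almost nothing and keeps every participant who has outcome data.

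**What to change.** In SAP 5.2, before the randomisation codes are released:

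- State that, for covariate use only, a missing baseline adherence value is replaced by the mean over all randomised participants, ignoring arm. Alternatively, add baseline to the multiple imputation model. Apply the same rule to baseline rescue-free days.
- Say whether the 14 days are calendar days or days without a device incident, and use the same wording in Table 5.
- Report, by arm, the number of participants whose baseline was missing, beside the number analysed and the ITT number.

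The cost is a few sentences and a footnote. A mean-filled baseline gives slightly less precision gain than a measured one, but because the variable is pre-randomisation and the fill ignores arm, it does not bias the treatment contrast.
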